- a. Study design, including the sequence and timing of study procedures (distinguish research procedures from those that are part of routine care).
 - b. Study duration and number of study visits required of research participants.
 - c. Blinding, including justification for blinding or not blinding the trial, if applicable.
 - d. Justification of why participants will not receive routine care or will have current therapy stopped.
 - e. Justification for inclusion of a placebo or non-treatment group.
 - f. Definition of treatment failure or participant removal criteria.
 - g. Description of what happens to participants receiving therapy when study ends or if a participant's participation in the study ends prematurely.
- Prospective, randomized, controlled trial
 - One hundred twenty adult patients with closed fractures of the distal radius will be randomized to below-elbow, sugar-tong splinting versus short arm casting for immediate post-reduction immobilization.
 - Residents will undergo a teaching session specifically for instruction on sugar tong splinting versus short arm casting. On-call resident will have access to an electronic folder containing randomization of patient to sugar tong splint versus bivalved short arm cast. All reductions will be performed under local hematoma block with 1% lidocaine and traction and less than three attempts at reduction.
 - Patients will follow up at one, two and four weeks for repeat AP and lateral radiographs of the forearm to measure radiographic parameters to determine maintenance of reduction and will complete the Disabilities of the Arm, Shoulder and Hand Score (DASH) for functional scoring of the upper extremity at two weeks.
 - Maintenance of reduction, as defined below, will be compared between splint constructs overall and in stable versus unstable fractures in each immobilization group. Specific changes in radial height, radial inclination and volar tilt as continuous variables will also be compared, as will DASH scores measuring functionality.
 - Maintenance of reduction will be defined as: loss of reduction of < 2 mm radial height, < 5 degrees of radial inclination or < 10 degrees of volar tilt and/or < 2 mm intra-articular step off, in follow up radiographs as compared to immediate post-reduction radiographs (Koval et al., 2006).

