 - Unstable fractures will be defined as, at injury: > 4 mm radial shortening, > 10 degrees dorsal tilt, radial-ulnar translation of radius > 2 mm, dorsal comminution > 50% diameter of radius, > 2mm intra-articular displacement (Koval et al., 2006; Stoffelen and Broos, 1998). Fractures meeting these criteria will undergo ORIF after reduction and at a later time. However, reduction parameters and maintenance of reduction will be evaluated and compared for both splinting techniques until ORIF.

5. Inclusion/Exclusion Criteria

- Inclusion criteria: adult > 18 years of age, closed fracture, isolated injury, no prior injury to ipsilateral forearm, less than or equal to two attempts at reduction.

6. Drugs/ Substances/ Devices

- a. The rationale for choosing the drug and dose or for choosing the device to be used.
- b. Justification and safety information if FDA approved drugs will be administered for non-FDA approved indications or if doses or routes of administration or participant populations are changed.

- c. Justification and safety information if non-FDA approved drugs without an IND will be administered.

Not Applicable

7. Study Statistics

- a. Primary outcome variable.
- b. Secondary outcome variables.
- c. Statistical plan including sample size justification and interim data analysis.
- d. Early stopping rules.

Primary outcome variable: Maintenance of reduction

Secondary outcome variables: Radiographic parameters analyzed individually: radial height, radial inclination, volar tilt, DASH scores

Statistical plan including sample size: Sample size was calculated based on standard deviations for the above-noted outcomes variables reported in the literature and selected a sample size based on the largest calculated sample size. This was increased from 167 to 200 to account for expected dropout.

Early stopping rules: Less than 50% patient follow-up.

8. Risks

- a. Medical risks, listing all procedures, their major and minor risks and expected frequency.
- b. Steps taken to minimize the risks.
- c. Plan for reporting unanticipated problems or study deviations.
- d. Legal risks such as the risks that would be associated with breach of confidentiality.
- e. Financial risks to the participants.
 - No medical risks outside of standard of care.
 - Patients will be treated with standard of care.
 - Research committee of Department of Orthopaedic Surgery follows the progress of the project.
 - No legal risks.
 - No financial risks.

9. Benefits

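### The planned stability analysis does not test whether the cast-versus-splint difference depends on fracture stability; estimate that directly, label it exploratory, and adjust the overall comparison for stability at injury

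*Combined protocol and SAP*

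**What the plan says.** The primary outcome is given in Section 7 (Study Statistics): "Primary outcome variable: Maintenance of reduction". How it is to be compared is described in Section 4 (Study Procedures): it "will be compared between splint constructs overall and in stable versus unstable fractures in each immobilization group".

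Stability is classified on the injury findings. The definition opens "Unstable fractures will be defined as, at injury: > 4 mm radial shortening, > 10 degrees dorsal tilt" and goes on to list translation, comminution and intra-articular displacement, five criteria in all, without saying whether any one or all must be met. The same bullet adds "Fractures meeting these criteria will undergo ORIF after reduction and at a later time" and then, for these fractures, "reduction parameters and maintenance of reduction will be evaluated and compared for both splinting techniques until ORIF".

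On allocation, Section 4 says only that patients "will be randomized to below-elbow, sugar-tong splinting versus short arm casting" and that "On-call resident will have access to an electronic folder containing randomization of patient to sugar tong splint versus bivalved short arm cast". No strata, blocks or ratio are described. No statistical test, covariate, stratified analysis or interaction term is named anywhere in the document.

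**The concern.** The trial is meant to guide the choice of construct. The useful question about stability is therefore whether the cast-versus-splint difference is the same in stable and unstable fractures. A comparison of stable with unstable fractures within the cast arm, and another within the splint arm, answers something else: whether unstable fractures lose reduction more often. Neither contrast is protected by randomisation.

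Reporting two such tests, one per arm, invites the reader to treat a significant result in one arm and a non-significant result in the other as evidence that the constructs behave differently. That pattern is common by chance when each test has moderate power, even if the construct effect is identical in both strata. Reading the sentence instead as a separate arm comparison in each stratum is better, because each comparison is randomised, but two separate tests still do not estimate a difference in effect.

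The wording also supports two different analyses, so the choice could be made after the data are seen.

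**Working it through.** **Inputs.** From the documents: a binary primary outcome, two arms, and 120 patients (Section 4) or 167 raised to 200 (Section 7, not stated whether total or per arm). These sizes conflict and are used here as alternative totals. Not in the documents and therefore assumed: two-sided 5% tests, 1:1 allocation, an unstable share of 30% to 70%, and maintenance of 80% to 90% in stable and 50% to 80% in unstable fractures. The plan states no figure of its own for the stability analysis, so there is none to reproduce.

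**1. Literal reading: stable versus unstable within each arm.** Suppose there is no construct effect and no interaction. The two within-arm tests are then independent with the same power p, and the chance that exactly one is significant is 2p(1 − p).

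Example: 120 patients, half unstable (30 per cell), 85% versus 60%, pooled rate 72.5%.
- Pooled SE = √(2 × 0.725 × 0.275 / 30) = 0.115.
- Unpooled SE = √((0.85 × 0.15 + 0.60 × 0.40) / 30) = 0.111.
- p ≈ Φ((0.25 − 1.96 × 0.115) / 0.111) ≈ 0.59.
- 2 × 0.59 × 0.41 ≈ 0.48.

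Simulation gives 48% at 120. At 167 it gives p = 0.74 and 38% (2 × 0.74 × 0.26 = 0.385).

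Simulated chance of significance in exactly one arm, half unstable, no true interaction:

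| Maintained, stable / unstable | N = 120 | N = 167 | N = 200 |
|---|---|---|---|
| 80% / 80% | 9% | 9% | 10% |
| 80% / 70% | 25% | 30% | 33% |
| 80% / 60% | 48% | 50% | 48% |
| 80% / 50% | 43% | 28% | 19% |
| 90% / 50% | 10% | 2% | 1% |

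Over unstable shares of 30% to 70% the range is again about 1% to 50%. It is low when stability has no effect (p near 5%) or a very large one (p near 100%), and peaks where p is near one half. A direct test of interaction on the log odds ratio was falsely positive in about 1% to 5% of the same simulated trials.

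**2. Between-construct reading: cast versus splint within each stratum.** With no construct effect each test has p ≈ 0.05, so significance in exactly one stratum has probability 2 × 0.05 × 0.95 = 0.095. Simulation gives about 7% to 10% across the settings tried.

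**3. What an interaction test could detect.** Take a 20-point construct effect confined to unstable fractures: 80% in both arms when stable, 60% versus 40% when unstable, half unstable.
- N = 120 (30 per cell): SE = √((2 × 0.16 + 2 × 0.24) / 30) = 0.163; power ≈ Φ(0.20 / 0.163 − 1.96) = 23%.
- N = 200 (50 per cell): SE = √(0.80 / 50) = 0.126; power ≈ 35%.

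**4. Chance imbalance in the overall comparison.** With simple randomisation and half unstable, the 95% range of the between-arm difference in unstable share is ±1.96 × √(2 × 0.25 / 60) = ±18 points at 120, and ±15 at 167. At a 25-point stability gap, an imbalance at that limit moves the crude difference by 0.18 × 25 ≈ 4.5 points (0.15 × 25 ≈ 3.8 at 167). The crude 95% half-width at 120 is 1.96 × √(2 × 0.725 × 0.275 / 60) = 16 points, which already allows for this. In this scenario stability explains 0.25² × 0.25 / (0.725 × 0.275) ≈ 8% of the outcome variance, so the precision gain from adjustment is modest.

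**The case against.** The sentence in Section 4 begins with a comparison between constructs, and the later statement that unstable fractures "reduction parameters and maintenance of reduction will be evaluated and compared for both splinting techniques until ORIF" is plainly a between-technique comparison. Together they can be read as planning the arm comparison by stability, and the striking percentages do not apply to that reading. This stands. It lowers the chance of a misleading pattern to about 10%, but it does not supply a test of whether the effects differ.

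A reader might infer that the plan will often produce a false claim that one construct suits only stable fractures. The documents do not support that. They nowhere say that significance in one arm and not the other will be taken as a difference between constructs. The research hypothesis in Section 1 concerns the overall comparison, and the frequency rests on rates the documents do not give. If 167 were the number per arm, the 85%/60% example would fall to 8%.

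A reader might also infer that leaving stability out of the randomisation and the main analysis biases the primary result. That does not follow either. The protocol is silent on both methods rather than excluding stability, and chance imbalance has expectation zero and is covered by valid unadjusted inference.

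Finally, changing the analysis is not entirely free. Interaction power is low, the instability criteria lack a combining rule, and unstable fractures are observed only until ORIF.

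**Conclusion.** The concern holds in a limited form. As written, the stability analysis is open to two readings, and neither estimates how the construct effect differs by stability. The literal reading is a non-randomised contrast that does not address the choice of construct.

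The figures in the working show how misleading side-by-side reading could be. They rest on assumed maintenance rates, an assumed unstable share and sample sizes taken as totals; they do not predict what this trial will report. Adjusting the overall comparison for stability is worth doing for a modest gain in precision and protection against an unlucky split. It does not correct a bias. This is a change that should be made, but the primary comparison is not invalid without it.

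**What to change.** 1. Replace the within-arm contrast with the cast-versus-splint difference in maintenance of reduction and its 95% CI in each stability stratum, plus one construct-by-stability interaction estimate with its CI. Label this exploratory and say that its power is low, so that a non-significant interaction is not read as evidence of equal effects.
2. Adjust or stratify the overall comparison by stability at injury, using a Mantel-Haenszel risk difference or a stability term in the model, and state this before the data are examined.
3. To make both workable, state whether any or all of the Section 4 criteria define an unstable fracture, and compare the arms over the same pre-ORIF observation window, because follow-up for maintenance is cut short in unstable fractures.

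Items 1 and 2 are wording changes and need no extra patients or visits. Item 3 needs a decision by the investigators and consistent recording of the injury findings and the date of ORIF. Separate randomisation lists by stability are optional. They would require classification before the allocation is opened, and blocked lists in a folder open to the on-call resident could make the next allocation easier to predict.

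### No adjustment for the immediate post-reduction value is specified when radiographic changes are compared between arms; a baseline-adjusted model would be at least as precise in large samples and would remove conditional imbalance

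*Combined protocol and SAP*

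**What the plan says.** Section 4 (Study Procedures) sets out the continuous comparison: "Specific changes in radial height, radial inclination and volar tilt as continuous variables will also be compared". The only reference film named is in the definition of maintenance of reduction, which judges loss "in follow up radiographs as compared to immediate post-reduction radiographs"; for the continuous changes the same reference is implied. Section 4 also defines unstable fractures by their features at injury and plans to compare maintenance of reduction by stability, so stability will be recorded. Unstable fractures go on to ORIF and are evaluated only up to that operation.

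Section 7 (Study Statistics) gives the status of the outcomes: "Primary outcome variable: Maintenance of reduction", and "Secondary outcome variables: Radiographic parameters analyzed individually: radial height, radial inclination, volar tilt, DASH scores". This list names the parameters, not their changes. The statistical plan consists of a sample-size statement alone: "Sample size was calculated based on standard deviations for the above-noted outcomes variables reported in the literature", and "This was increased from 167 to 200 to account for expected dropout". Section 4 gives a different number: "One hundred twenty adult patients with closed fractures of the distal radius will be randomized".

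No section names a test, a model or a covariate for any outcome. No section says whether the post-reduction film is taken before or after allocation, or before or after the cast or splint is applied.

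**The concern.** As written, the planned comparison is a difference in mean change between arms. Subtracting the post-reduction value is itself a form of adjustment, but with the slope fixed at 1. If the true slope of the follow-up value on the post-reduction value is not 1, two things follow. The change score carries avoidable noise, so its confidence interval is wider than the same data allow. And if one arm happens to start with better reductions, part of that imbalance stays in the estimated difference.

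Three of the four secondary outcomes are affected, and changes in radiographic parameters also appear in the research hypothesis in Section 1. That hypothesis is one of no significant difference, which an imprecise comparison makes easier to reach. Narrow intervals therefore matter here more than usual.

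**Working it through.** **The plan's own figure.** The 167 cannot be reproduced, because alpha, power, the difference sought and the SDs are not given. The step to 200 can: 167/(1 − 0.165) = 200, or 167 × 1.20 = 200.4. It fits about 16.5% dropout by division or about 20% by multiplication; the rate is not stated. The 120 in Section 4 matches neither 167 nor 200, so all three are carried below.

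**Assumed inputs.** The correlation r between post-reduction and follow-up values, the ratio k of follow-up SD to post-reduction SD, and 1:1 allocation. The documents give none of these.

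**Precision.** Take the post-reduction SD as 1.

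- Variance of the change score: 1 + k² − 2rk
- Variance after adjustment: k²(1 − r²)
- Change-score variance minus adjusted variance: 1 − 2rk + r²k² = (1 − rk)²

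The difference is a square, so it cannot be negative, and it is zero only when rk = 1. The variance ratio, adjusted over change, is k²(1 − r²)/(1 + k² − 2rk). With k = 1 it reduces to (1 + r)/2:

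| r (k = 1) | Variance ratio | Reduction | 120 act like | 167 act like | 200 act like |
|---|---|---|---|---|---|
| 0.5 | 0.75 | 25% | 160 | 223 | 267 |
| 0.7 | 0.85 | 15% | 141 | 196 | 235 |
| 0.8 | 0.90 | 10% | 133 | 186 | 222 |
| 0.9 | 0.95 | 5% | 126 | 176 | 211 |

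The last three columns are N divided by the ratio. Interval width scales with the square root of the ratio: √0.75 = 0.87 (13% narrower) and √0.95 = 0.97 (about 3% narrower).

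The result is sensitive to k:

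- k = 1.25, r = 0.8: 1.5625 × 0.36 = 0.5625, over 1 + 1.5625 − 2.0 = 0.5625, ratio 1.00. Here rk = 1 and nothing is gained.
- k = 1.25, r = 0.5: ratio 0.89.
- k = 1.5, r = 0.5: 1.6875/1.75 = 0.96.
- k = 1.5, r = 0.7: 1.1475/1.15 = 1.00.
- k = 1.5, r = 0.9: ratio 0.78. Here rk = 1.35, and the change score loses precision because its slope is too low.

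**Conditional imbalance.** The 95% range of the chance difference in mean post-reduction value is ±1.96 × √(2/n), with n per arm. The change-score difference carries (rk − 1) times this: a fraction 1 − rk with reversed sign when rk < 1.

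| n per arm (total) | Chance imbalance, 95% range | Carried over at k = 1, r = 0.5 | r = 0.7 | r = 0.9 |
|---|---|---|---|---|
| 60 (120) | ±0.36 SD | 0.18 | 0.11 | 0.04 |
| 83 (167) | ±0.30 SD | 0.15 | 0.09 | 0.03 |
| 100 (200) | ±0.28 SD | 0.14 | 0.08 | 0.03 |

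Entries are in SDs of the post-reduction value. With rk = 1 every carry-over entry is zero. The further gain from stability at injury has not been quantified, because the documents give no figures for it.

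**The case against.** The strongest reply is that the plan is silent rather than wrong. Section 4 says only that changes will be compared, and an adjusted comparison of changes fits that wording. A reader might infer that the sponsor has chosen an unadjusted analysis and ruled out covariates; the documents do not say that. This stands, and it is why the point is that adjustment is unspecified. It does not remove the point: if adjustment is intended, the same sentence is needed.

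Second, the loss is not certain. A reader might take the k = 1 figures as the actual cost. Spread may grow as fractures displace, and if loss of reduction is unrelated to the post-reduction value then rk = 1 and the change score loses nothing. This also stands. What remains is that the adjusted model estimates the slope instead of assuming it, for a few degrees of freedom.

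Third, the post-reduction value may not be a pre-randomization covariate. Section 4 gives the on-call resident access to the allocation folder and does not say that reduction and its film come first. If the film follows allocation or is taken in the construct, an imbalance need not be chance and adjusting for it would need justification. This stands as a condition on the fix. It bears on the change score too, which uses the same film.

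Fourth, patients with unstable fractures are followed only until ORIF, so some will have no usable film at a later visit. The model does not solve this; the plan has to say which films count.

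**Conclusion.** The point holds as a recommended improvement to three secondary outcomes. The direction is secure: in large samples the adjusted model is never less precise than the change score, and the reference value is already required. The size is an assumption. The variance saved is 5% to 25% for r from 0.9 down to 0.5 with k = 1, and falls to zero where r·k = 1. The imbalance carried into the result at k = 1 and r = 0.7 is up to about 0.11 SD with 60 per arm and 0.08 SD with 100 per arm.

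Three stronger readings are not supported. A reader might infer that the change comparison is biased; if the film precedes allocation it is unbiased over repeated randomization, and the issue is precision and conditional imbalance. A reader might suppose that poorly reduced fractures have less reduction to lose, so that the slope must be below 1; nothing in the documents establishes that. And a reader might extend the argument to the primary outcome; that outcome is binary, these calculations do not cover it, and no covariates are proposed for it here.

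**What to change.** Add to Section 7:

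1. For each of the three parameters, at a named visit (the hypothesis in Section 1 points to two weeks), fit a linear model of the change, or equivalently the follow-up value, on construct, the immediate post-reduction value of that parameter, and stable/unstable status at injury. Report the adjusted difference between arms with its 95% CI.
2. State whether the reference film is taken before or after allocation and application of the cast or splint. If after, adjust for stability at injury alone in the main model and give the post-reduction-adjusted result as a sensitivity analysis.
3. State that films taken after ORIF are not used, in line with Section 4.

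The conflict between 120 and 167/200 must be reconciled separately, since it sets the precision available under either analysis.

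The cost is a few degrees of freedom, a few sentences and slightly more analysis work. No new data, visits or patients are needed. Naming the model in advance also removes the option of choosing between adjusted and unadjusted results once they are known.

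### The only primary outcome, maintenance of reduction, has no determinate rule for combining its four radiographic limits, and read literally it counts fractures that break two or three limits as maintained

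*Combined protocol and SAP*

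**What the plan says.** Section 7 (Study Statistics) names a single primary outcome: "Primary outcome variable: Maintenance of reduction". Its only definition is in section 4 (Study Procedures). It opens with "Maintenance of reduction will be defined as: loss of reduction of < 2 mm radial height" and, after a comma, continues "< 5 degrees of radial inclination or < 10 degrees of volar tilt and/or < 2 mm intra-articular step off". Change is measured from the immediate post-reduction film. The definition cites a published trial but does not reproduce a combination rule from it.

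Four other places might have settled the rule, and none does:

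- The form's prompt for a definition of treatment failure (section 4, item f) has no separate answer.
- The 'Primary objectives' line in section 2 has no text under it.
- The other list of radiographic criteria, for unstable fractures at the end of section 4, is separated by commas with no connective, as in "dorsal comminution > 50% diameter of radius, > 2mm intra-articular displacement". It offers no convention to borrow.
- The secondary outcomes in section 7 are "Radiographic parameters analyzed individually: radial height, radial inclination, volar tilt, DASH scores". They give no combination rule and omit step-off.

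Section 5 does not exclude extra-articular fractures, and the definition does not say how step-off is scored in them.

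**The concern.** An 'or' between limits suits a definition of loss of reduction, where exceeding any one limit is failure. Maintenance is the complement of that, so its conditions must be joined by 'and'. The protocol defines maintenance but uses 'or' and 'and/or'. Taken literally, a fracture that has lost too much height, inclination and tilt could still count as maintained because its step-off is under 2 mm.

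This rule decides who is a success on the only primary outcome. With the rule open, the same radiographs can give different primary results, and the choice could be made after the data are seen. The direction also matters. The hypothesis in section 1 is that the arms do not differ significantly, and a lenient rule pushes both arms towards 100%, which shrinks any difference between them.

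**Working it through.** **Inputs from the document.** Four conditions, each met or not met: A, height loss under 2 mm; B, inclination loss under 5 degrees; C, tilt loss under 10 degrees; D, step-off under 2 mm. The connectives are A, B or C and/or D. The plan states no maintenance rate or power, so there is no figure of its own to reproduce.

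**Step 1: enumeration (no assumptions).** There are 2⁴ = 16 patterns.

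| Rule | Patterns called maintained | Most limits that can be broken |
|---|---|---|
| Any: A or B or C or D | 2⁴ − 1 = 15 | 3 |
| Mixed: (A or B or C) and D | (2³ − 1) × 1 = 7 | 2 |
| All: A and B and C and D | 1 | 0 |

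The first two rules take the 'or' as written and resolve 'and/or' as 'or' and as 'and'. The third reads the sentence as a list of tolerances, all to be respected. Other groupings of the same connectives give 13, 9, 5 or 3 patterns. If an extra-articular fracture is counted as meeting D, 8 patterns remain, and the three rules accept 8, 7 and 1 of them.

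**Step 2: illustrative rates (assumed inputs).** Let each limit be exceeded with probability p, and let the four measures share a common correlation ρ through one normal factor z. With t = Φ⁻¹(1 − p), the chance of staying within a limit given z is m = Φ((t − √ρ·z)/√(1 − ρ)), and e = 1 − m. Averaging over z:

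- any = E[1 − e⁴]
- mixed = E[(1 − e³)·m]
- all = E[m⁴]

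At p = 0.20 and ρ = 0 these are 1 − 0.2⁴ = 0.998, (1 − 0.2³) × 0.8 = 0.794 and 0.8⁴ = 0.410. Over the range of ρ:

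| ρ | Any | Mixed | All |
|---|---|---|---|
| 0 | 99.8% | 79.4% | 41.0% |
| 0.3 | 98.5% | 78.6% | 49.7% |
| 0.5 | 96.7% | 78.3% | 55.6% |
| 0.7 | 93.7% | 78.3% | 62.0% |

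For p from 10% to 30%, the ranges are 88–99.99%, 67–90% and 24–78%.

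**Step 3: patients who change class at p = 0.20.** Each rule's maintained set contains the next, so the number changing class is N times the difference in rates. Section 4 gives 120 ("One hundred twenty adult patients with closed fractures of the distal radius will be randomized"). Section 7 gives a different size ("This was increased from 167 to 200 to account for expected dropout"); that discrepancy is a separate matter, so results are shown for 120 and for 167, the number before the dropout allowance.

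- Any versus all: 120 × (0.998 − 0.410) = 71 at ρ = 0, and 120 × (0.937 − 0.620) = 38 at ρ = 0.7. With 167 patients, the range is 53 to 98.
- Mixed versus all: 120 × (0.794 − 0.410) = 46 at ρ = 0, and 120 × (0.783 − 0.620) = 20 at ρ = 0.7. With 167 patients, the range is 27 to 64.

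**Step 4: effect on the arm comparison.** Assume 15% exceedance on every measure in one arm and 30% in the other, with ρ from 0 to 0.7. The difference in maintenance is 1–8 points under 'any', 16–17 under 'mixed' and 21–28 under 'all'.

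**Step 5: step-off always met, as if every fracture were extra-articular.** At p = 0.20, 'any' becomes 100%, 'mixed' 92–99% and 'all' 51–66%. The arm difference of Step 4 under 'mixed' falls to 2–9 points.

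**The case against.** The strongest reply is that the readings are not equally plausible. An orthopaedic reader would take the sentence as a list of tolerances, none to be exceeded, and scoring by 'any' would defeat the meaning of the word maintenance. Nothing suggests that the investigators would do so, and the largest contrasts above compare 'any' with 'all'. The cited trial may also fix the rule.

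Much of this is fair. 'All' is the sensible reading, and the ceiling argument applies only if a lenient rule is used. But 'all' requires a written 'or' to be read as 'and', so if it was intended, the sentence misstates it. The cited trial's rule is not in the document. The mixed reading, one of the two that 'and/or' expressly allows, also differs substantially from 'all'.

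A second objection is that the rates are invented: equal exceedance for four different measures, a common correlation, and every fracture at risk of step-off. That stands. The percentages are illustrative and do not bound what this trial will see. With step-off always met, however, the gap between 'mixed' and 'all' widens rather than closes.

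Third, height, inclination and tilt are also analysed individually, whatever the connective, and the stored measurements can be rescored under any rule. This is partial mitigation only. Those analyses are secondary and omit step-off, and the ability to rescore is the reason to fix the rule in advance.

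**Conclusion.** The concern holds, and the definition must be corrected before analysis. As written it does not determine a single rule, and its literal readings classify fractures that break two or three limits as maintained. The counts of 15, 7 and 1 out of 16 rest on the wording alone, and the conclusion rests on them and on this being the sole primary outcome. The rates, reclassification counts and arm differences depend on assumed inputs and show only that the choice of rule could matter a great deal. The ordering of the three rules does not depend on those inputs. The plan states no power, so no loss of power against a target is claimed.

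**What to change.** Keep the cut-offs and the reference film, and replace the sentence in section 4 with wording such as:

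> Reduction is maintained if, relative to the immediate post-reduction radiograph, the loss is < 2 mm in radial height AND < 5 degrees in radial inclination AND < 10 degrees in volar tilt AND, in intra-articular fractures, step-off is < 2 mm. Reduction is lost if any one applicable limit is reached or exceeded.

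The word 'loss' should stay, so that improvement is not scored as failure. The investigators should confirm that this is the rule they intended, including that step-off does not apply to extra-articular fractures, because the document does not say so.

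The cost is two or three sentences and no new data. The one drawback is that the reported maintenance percentage will be lower than under the literal 'or'.

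This settles the combination rule only. Section 4 schedules several films ("Patients will follow up at one, two and four weeks for repeat AP and lateral radiographs"), and which of them decides the primary outcome has to be specified separately.
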